## 1. Purpose - in nontechnical, lay language

a. Summarize the purpose and objectives of this protocol in one short paragraph. There are over 7 million people living with stroke in the United States. Per year, approximately 17,000 veterans are admitted to the VA for acute stroke. Chronic pain after stroke can occur between 10-50% of stroke survivors. Post-stroke pain (PSP) can lead to further complications in a stroke survivor's recovery. Exercise has improved PSP and associated symptoms such as mobility, fatigue, and quality of life. Repetitive transcranial magnetic stimulation (rTMS) is a noninvasive technique using electromagnetic induction for cortical neurostimulation. The use of rTMS has been explored shown to be effective in treating chronic PSP but is limited in effect duration. Our proposal will test the hypothesis that rTMS is feasible and safe to be paired with exercise. Additionally, we believe a complementary effect can develop to enhance the neurostimulation duration of rTMS.

b. Describe how outcomes will be measured for this protocol. We will collect outcome measures as listed in Table 1: Schedule of Events below. Additionally, we will collect feasibility metrics (recruitment, refusal, attrition and retention rates) and safety outcomes. Finally, neuroimaging will be obtained and we will perform structural and functional connectivity analysis of the pre- and post-intervention imaging.

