### 3. Participants (Screening and Selection)

a. How many participants are to be enrolled?

Up to 100 patients will undergo the screening process. Our goal is to enroll 32 patients. We anticipate having to randomize 36 patients to reach the anticipated 32 patients that complete the study in entirety.

b. Describe the characteristics of anticipated or planned participants (if multiple groups, repeat list for each group).

Sex: both

Race/Ethnicity: all

Age: 19-89

Health status: stroke patients with headaches

c. From what population(s) will the participants be derived? Patients with stroke and headaches presenting to the Birmingham VA hospital will be recruited.

Describe your ability to obtain access to the proposed population that will allow recruitment of the necessary number of participants: [name] is a stroke neurologist at the BVAMC and has access to all stroke patients admitted to the BVAMC.

d. Describe the inclusion/exclusion criteria:

Inclusion Criteria: 1) Male or female Veteran of US military  $\geq 19$  years of age; signed informed consent; 2) Minimum of 3-months since time of stroke and medically stable; 3) Headache has persisted for  $> 3$  months after stabilization of the stroke; 4) Ability to walk or tolerate recumbent cycle ergometry for 10 mins

without assistance; 5) Stable pain medication regimen for ≥1 month prior to study; 6) Females of child-bearing potential (i.e. not postmenopausal or surgically sterile) must be using a medically acceptable method of birth control and should not be pregnant nor have plans for pregnancy or breastfeeding during the study; 7) Completed diagnostic, maximal graded exercise test including 12-lead ECG and indirect calorimetry (i.e. oxygen uptake, minute ventilation, respiratory exchange ratio, etc.), and cleared for participation by an nurse research coordinator; 8) Minimum pain intensity of 30 on the Mechanical Visual Analogue Scale on average with pain symptoms.

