Exclusion Criteria: 1) Moderate to severe cognitive impairment (Montreal Cognitive Assessment score <16/30); 2) Pre-stroke modified Rankin >2; 3) History of seizures; 4) Presence of any standard TMS or MRI contraindications (see human subjects); 5) Current diagnosis of DSM-5-defined bipolar disorder I, schizophrenia, schizoaffective disorder, or obsessive-compulsive disorder; 6) Diagnosis of moderate or severe substance use disorder (except for caffeine and nicotine) during the preceding 3 months (Participants must agree to abstain from illicit drugs during the study); 7) Increased risk of suicide that necessitates inpatient treatment or warrants additional therapy excluded by the protocol; and/or intensity of suicidal ideation (Type 4 or Type 5) or any suicidal behavior in the past 3 months on Columbia Suicide Severity Rating Scale (C-SSRS); 8) Litigating for compensation for a psychiatric disorder. Veterans who are in the process of applying for or receiving VA service-connected disability are eligible; 9) Current enrollment in another intervention trial for pain or stroke; 10) Persons imprisoned, of minor age, diagnosed with terminal illness, or require surrogate for consent; 11) Fails baseline exercise screening activities; 12) Persistent post-stroke headaches not better accounted for by another diagnosis; 13) Is unable to reliably attend intervention sessions i.e. planning to move, transportation issues; 14) Neurological disorder pre- or post-stroke affecting subject's ability to follow study directions.

e. If participants will comprise more than one group or stratification, describe each group (e.g., treatment/intervention, placebo, controls, sham treatment) **and** provide the number of participants anticipated in each group. Up to 100 patients will undergo the screening process. Our goal is to randomize 32 patients with 16 in the sham and 16 in the active rTMS group. We anticipate having to randomize 36 patients to reach the anticipated 32 patients.

f. Indicate which, if any, of the special populations listed below will be involved in the protocol. Include the Special Populations Review Form (SPRF) if indicated.

Pregnant Women: Attach [SPRF—Pregnant Women, Fetuses, Neonates/Nonviable Neonates](#)

Fetuses: Attach [SPRF—Pregnant Women, Fetuses, Neonates/Nonviable Neonates](#)

Neonates/Nonviable Neonates: [SPRF—Pregnant Women, Fetuses, Neonates/Nonviable Neonates](#)

Prisoners: Attach [SPRF—Prisoners](#)

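### Exclusion 13 selects for attendance before randomization, so attrition and retention describe only veterans judged able to attend, and the section 1.b rates are not defined to show who was turned away

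*Combined protocol and SAP*

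**What the plan says.** Section 1.a states the aim: "Our proposal will test the hypothesis that rTMS is feasible and safe to be paired with exercise". It also proposes that the pairing may prolong the effect of rTMS. Section 1.b says how feasibility will be described: "we will collect feasibility metrics (recruitment, refusal, attrition and retention rates) and safety outcomes". None of the four rates is given a numerator, a denominator or a success threshold.

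Section 3.d, exclusion 13, removes a person who "Is unable to reliably attend intervention sessions i.e. planning to move, transportation issues". There is no operational test of reliability, and the plan does not say at which step the item is applied.

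On numbers, section 3.a says "Up to 100 patients will undergo the screening process" and "We anticipate having to randomize 36 patients to reach the anticipated 32 patients that complete the study in entirety".

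On sequence, section 3.h mails a recruitment letter to patients already considered eligible and follows it with a call or email. Section 3.j starts formal screening with informed consent. Section 4.a randomizes only those who still meet the criteria.

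On burden, section 4.a describes supervised in-person exercise three times a week for 8 weeks, with rTMS on the same day before each session. The exercise paragraph of that section also gives a total of 10 sessions.

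**The concern.** For a supervised in-person regimen with repeated visits, travel and availability are an obvious barrier to feasibility. Item 13 takes people with that barrier out before randomization. Attrition and retention are then measured in those who remain. With no test of reliability, staff may also exclude anyone they expect to drop out, which would tend to raise the reported retention.

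What is at stake is how far the result carries. High retention could be read as showing that the paired regimen is feasible for veterans with post-stroke headache in general, when it was shown only for those expected to attend. Someone planning a later trial without such a criterion could randomize too few. Reasons for exclusion that are not recorded at the time cannot be reliably reconstructed later.

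**Working it through.** **1. The plan's own figure.** Section 3.a gives 36 randomized for 32 completers and states no dropout rate. The implied attrition is 4/36 = 11.1%, and retention is 32/36 = 88.9%. A 10% dropout also reproduces it: 32/(1 − 0.10) = 35.6, rounded up to 36. If 32 of 36 were observed, the exact 95% interval would be 73.9% to 96.9%. That interval covers sampling error among the randomized; it does not cover selection before randomization.

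**2. Where the selection falls.** Item 13 is an eligibility criterion (3.d), and randomization follows eligibility (4.a). A retention rate among the randomized is therefore conditional on having been judged able to attend.

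**3. Whether another rate would show the loss.** This depends on definitions that section 1.b does not give.
- If item 13 is applied after consent, a recruitment rate of randomized over screened would fall. At the cap it is 36/100 = 36%, leaving 100 − 36 = 64 not randomized for any reason.
- If item 13 is applied at record review before the letter, or during the call, the person may never enter the 100.
- A refusal rate might or might not include a veteran who says on the telephone that travel is impossible.

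**4. Size of the overstatement.** Let f be the share of otherwise eligible people removed by item 13, and r_u the retention they would have had. The documents give neither, so both are assumed. Holding retention in the selected group at 88.9%:

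- retention without the selection = (1 − f) × 0.889 + f × r_u
- overstatement = f × (0.889 − r_u)

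| f | r_u | Retention without selection | Overstatement (points) | Randomized for 32 completers |
|---|---|---|---|---|
| 5% | 0% | 84.4% | 4.4 | 38 |
| 5% | 50% | 86.9% | 1.9 | 37 |
| 10% | 0% | 80.0% | 8.9 | 40 |
| 10% | 50% | 85.0% | 3.9 | 38 |
| 20% | 0% | 71.1% | 17.8 | 45 |
| 20% | 50% | 81.1% | 7.8 | 40 |
| any | 88.9% | 88.9% | 0 | 36 |

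**5. A combined figure.** With k people excluded for attendance reasons, completers over randomized plus excluded is 32/(36 + k). For k = 4 this is 32/40 = 80.0%, the same as the row f = 4/40 = 10%, r_u = 0. The ratio always sets r_u to zero, so it is a lower bound and not an estimate.

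**6. The burden.** Three sessions a week for 8 weeks is 3 × 8 = 24 sessions. The same section states 10. Section 4.h ties payments to visits 5 and 10. Until these agree, the schedule against which item 13 judges attendance is not fixed.

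**The case against.** The strongest reply is that an attendance criterion is a reasonable conduct choice for a supervised in-person programme, and that retention among eligible people is the right figure for a later trial with the same criterion. That stands. The point concerns generalizability and reporting; it is not an internal error.

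A second reply is that recruitment and refusal are also named measures and can carry the loss. That stands in part. A reader might infer that none of the four rates can count a person turned away under item 13. The documents do not support that, because they leave all four undefined. For the same reason they do not ensure that the loss will be seen.

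A reader might also infer that a later trial would overestimate uptake. That does not follow from retention: uptake is informed by recruitment and refusal.

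Finally, one might ask that item 13 be applied last, so that people excluded by it alone can be identified. The objection to this is sound. It would take people already known to be unable to attend through consent, imaging and a maximal exercise test, and some could not travel to those procedures. A planned relocation also says little about whether the regimen is feasible and should not be counted with transport problems.

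**Conclusion.** The point holds as a limit on what the feasibility rates can show. Attrition and retention will describe veterans pre-selected for attendance, and they can overstate retention in the wider post-stroke headache population. The direction rests on the assumption that excluded people would drop out more often. Under the assumed ranges the overstatement is 1.9 to 17.8 points; if excluded people would be retained equally well, it is zero. The documents allow no narrower statement.

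A reader might go further and conclude that the trial will overstate feasibility. The documents do not support this: the number excluded and their likely retention are unknown, and a recruitment rate over everyone approached could show part of the loss. Nor is feasibility the only question, since safety and a complementary effect are also named.

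The change is worth making before recruitment because it is cheap and bears on the trial's first stated hypothesis.

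**What to change.** - **Section 3.d:** keep item 13 and its place in the screening sequence.
- **Screening log:** from the record review before the recruitment letter onward, record each person excluded under item 13 with the reason. Keep transport or schedule separate from relocation.
- **Section 1.b:** define the denominator of each of the four rates. Report the number excluded under item 13, by reason and as a share of those assessed, beside retention among the randomized. If a combined figure is shown, such as completers over randomized plus attendance-related item 13 exclusions, label it a lower bound.
- **Conclusion:** state feasibility as applying to veterans able to attend the in-person schedule.
- **Section 4.a:** reconcile three sessions a week for 8 weeks with the stated total of 10, and check the payment visits in section 4.h against the result.

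The cost is one log field, a few sentences in section 1.b and a small recording burden. Item 13 needs no change to treatment, visits or sample size. The feasibility picture may look less favourable.

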**Screening:** The screening procedure includes informed consent, vital signs, demographics, medication history, neurologic and psychiatric diagnostic evaluation, imaging studies, and medical history. Participants return for the baseline visit (within 2 to 30 days of screening). All potential participants will need to pass an Exercise Tolerance Test before randomization at the baseline visit. The test includes maximal graded exercise test including 12-lead ECG and indirect calorimetry (i.e. oxygen uptake, minute ventilation, respiratory exchange ratio, etc.), and clearance for participation by an Certified Registered Nurse Research Coordinator using established Exercise Clearance criteria followed the UAB Exercise Center.

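### Section 3.e sets a goal of 32 randomized, against 36 randomized and 32 completing in its own next sentence and in section 3.a

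*Combined protocol and SAP*

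**What the plan says.** The numbers appear in two items of section 3, Participants (Screening and Selection).

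- **Section 3.a (how many are to be enrolled).** The screening ceiling is 100. The goal is then given as "Our goal is to enroll 32 patients", followed by "We anticipate having to randomize 36 patients to reach the anticipated 32 patients that complete the study in entirety".
- **Section 3.e (groups and number per group).** The same ceiling is repeated, then "Our goal is to randomize 32 patients with 16 in the sham and 16 in the active rTMS group", then "We anticipate having to randomize 36 patients to reach the anticipated 32 patients". This last sentence does not say that the 32 are those who complete.

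On the order of events, section 3.j lists informed consent among the screening procedures and adds: "All potential participants will need to pass an Exercise Tolerance Test before randomization at the baseline visit". Section 6.a requires exercise-test clearance before a patient enters the trial. No section states a dropout rate, a split by arm for 36, or in so many words the count at which recruitment ends.

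**The concern.** The number 32 is used for three different things: patients enrolled, patients randomized and patients completing. The number randomized is given as both 32 and 36. If anyone is lost after randomization, and the plan expects some loss, 32 cannot be both the number randomized and the number completing.

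The conflict is in the item that exists to fix the group sizes, and the only arm sizes given (16 and 16) are attached to the lower number. Someone who sets up the randomization from section 3.e alone would plan for 16 + 16 and stop there. The trial would then be expected to fall short of its own completion target.

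**Working it through.** **Inputs**

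- Randomized: 36 (sections 3.a and 3.e); also 32 as 16 + 16 (section 3.e, goal).
- Completing: 32 (section 3.a).
- Enrolled: 32 (section 3.a, goal).
- Dropout rate: not stated.

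**Step 1. Can the 36 be reproduced?** Not from stated inputs, because no dropout rate is given. Back-solving from the pair: loss = 1 − 32/36 = 4/36 = 11.1%. In the other direction, number to randomize = 32/(1 − d), rounded up. An assumed d of 10% gives 32/0.90 = 35.6, so 36. The pair is therefore coherent as 36 randomized and 32 completing, at an assumed loss of 10 to 11%.

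**Step 2. What if the stated goal of 32 randomized is followed?** Expected completers = 32 × (1 − d). At the implied loss this is 32 × 32/36 = 28.4, or 14.2 per arm with equal loss in the two arms. Because d is not stated, a range is shown:

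| Assumed loss d | Randomized needed for 32 completers | Completers if 32 are randomized |
|---|---|---|
| 5% | 34 | 30.4 |
| 10% | 36 | 28.8 |
| 11.1% (implied) | 36 | 28.4 |
| 15% | 38 | 27.2 |
| 20% | 40 | 25.6 |

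At every loss in this range, 32 randomized gives fewer than 32 completers.

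**Step 3. Can 32 be the number enrolled?** The documents do not define enrolled. If it means consented, it comes at screening, before randomization, and must be at least 36. If it means randomized, it equals 36. Neither gives 32.

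**Step 4. Arm sizes.** The 16 + 16 split is 1:1. Carried over to 36 it gives 18 + 18, and 18 × 32/36 = 16 completers per arm, so the 16 + 16 fits as the expected number completing.

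**Illustration of scale only.** The documents state no significance level, power or effect size. Assuming a two-sided 5% level, 80% power and a normal approximation, the detectable difference is (1.960 + 0.842) × √(2/n) SD. This is 0.99 SD with 16 per arm and 1.06 SD with 14 per arm.

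**The case against.** The strongest reply is that the documents largely settle the matter. Both sections say that 36 will be randomized to reach 32, section 3.a says the 32 are completers, and the 36-to-32 step is ordinary allowance for dropout. On this view the fault is one verb in section 3.e and a loose use of enroll in section 3.a. Most of that stands: 36 randomized and 32 completing is clearly what was meant, and no sum fails. What does not follow is that nothing needs changing, because the explicit goal in section 3.e contradicts that reading in the item that sets the group sizes.

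Three stronger readings are tempting, and the documents do not support them.

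- **A completers-only analysis is planned, with the bias that would bring.** Planning for a number of completers says nothing about who is analysed, and no section proposes to restrict the analysis to completers.
- **The clash leaves attrition without a denominator.** Section 1.b does list "feasibility metrics (recruitment, refusal, attrition and retention rates" without defining them, but that gap would remain if section 3.e said 36. It is a separate missing detail.
- **The trial loses a stated amount of power.** There is no stated power to lose. Section 1.a gives feasibility and safety as the hypothesis to be tested, and nothing shows that a difference in SD units sized the trial.

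**Conclusion.** The randomization goal in section 3.e is wrong as written. It conflicts with the next sentence of the same item and with section 3.a, and the enrollment goal of 32 in section 3.a cannot stand beside 36 randomized. Taken literally, the goal of 32 would leave about 28 completers, about 14 per arm, some 3 to 4 short of the planned 32 (32 − 28.4 = 3.6). That shortfall rests on the back-solved loss of 11.1% and on recruitment actually stopping at 32, which the next sentence of section 3.e argues against. This is an error of wording in a sample-size statement. The underlying 36-to-32 plan is coherent. It should be corrected because it governs group sizes, but it does not call the design into question.

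**What to change.** State one set of numbers in both sections 3.a and 3.e: 36 randomized (18 active, 18 sham), with about 32 (16 + 16) expected to complete at about 11% attrition, and recruitment ending when 36 have been randomized. Replace the goal of enrolling 32 in section 3.a and the goal of randomizing 32 in section 3.e accordingly, and say in section 3.e that the 32 are completers. The 18 + 18 split assumes that the 1:1 allocation implied by 16 + 16 is kept. The sponsor should confirm the attrition figure, since it is inferred here and not stated in the protocol.

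The cost is an edit to two paragraphs. It needs no patients beyond the 36 already anticipated, stays within the screening ceiling of 100, and changes no procedure.

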#### **4. Protocol Procedures, Methods, and Duration - in nontechnical, lay language**

a. Describe the procedures for all aspects of your protocol. Tell us what you are doing.

Participants who continue to meet eligibility criteria are randomized into sham rTMS or active rTMS. Both groups receive exercise sessions. Schedule of events are shown in Table 1.

**Exercise sessions:** All participants will begin the exercise protocol for weeks 0-8. The 8-week standardized aerobic exercise training prescription progress from 20-minute to 40-minutes in-person sessions occurring 3 times per week on non-consecutive days (10 total sessions). Each session includes a combination of treadmill (TM) walking and stationary cycle ergometry (CE), and a combination of high-intensity interval training (HIIT) and moderate intensity steady-state exercise training (SST). Each session will be conducted under full supervision by a certified nurse at the BVAMC VA Therapy Gym. The exercise protocol has been successfully completed in multiple patient populations. Each exercise session begins with seated resting assessments for blood pressure (BP), heart rate reserve (HRR) and heart rate (HR), followed by 3-4 min warm-up at low intensity. Stopping rules: Exercise will be stopped due to inappropriate HR or BP responses, or at the participant's discretion. In cases where the participant reports intolerance or undue fatigue, workload adjustments (e.g., 10% reduction) may be made (and recorded) to encourage completion of the exercise session. Participant monitoring: Each individual session during supervised exercise training is monitored closely by a research nurse.

Outcome measures for subjects are collected per Table 1 schedule of Measures will be collected either while patients are in clinic during a standard of care visit at the VA Clinic, at a private preparation area either before or after their imaging at Highlands, at a private rTMS clinic room in the 7th Floor VA Neurology Clinic.

Data to be collected on subjects from the electronic medical record for this study includes demographics (sex, age, race, symptoms, medical history, smoking history, anatomical level/grade of intracranial stenosis); lab results, medications, inpatient records related to stroke, imaging results, and standard clinical assessment from rehabilitation stay and clinical visits.

- b.** What is the probable length of time required for the entire protocol (i.e., recruitment through data analysis to study closure)? 2 years
- c.** What is the total amount of time each participant will be involved? 3 months
- d.** If different phases are involved, what is the duration of each phase in which the participants will be involved? If no phases are involved, enter "None." none
- e.** List the procedures, the length of time the procedure takes, the total # of times the procedure is performed

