## 6. Risks - in nontechnical, lay language

a. List the known risks for participants as a result of participation in the research. This should not include the minimal risk of loss of confidentiality. However, it should include any physical, psychological, social, economic, and/or legal risks. If there is a greater than minimal risk of loss of confidentiality describe why this is so. Do not list risks associated with the standard-of-care procedures.

NOTE: Risks included here should be included in the consent form or information sheet, as applicable.  
 Physical Risks

rTMS: Although extremely rare, seizures have been described with rTMS, mainly in subjects who have a history of seizure. In some case reports, it was difficult to differentiate seizures from fainting or a convulsive syncope. The TMS coil makes noise, much like a loud pop when it produces its magnetic energy. Subject may or may not feel thumb twitch depending on the strength of the TMS pulse, but subject might also feel your facial muscles twitch slightly just around the eye. It is not painful. TMS can cause heating or movement of metallic objects in or near the head. In addition, the inactivation of pacemakers, medication pumps, cochlear prostheses and other implantable hardware may occur but subject with these metal implants are excluded from the study.

Exercise: Exercise Tolerance Testing: The risks of the exercise tolerance tests are minimal but could include fainting, falling, irregular heartbeat, and very rarely heart attack, stroke, or death (less than 1 in 2500 cases). Professional staff (clinically trained nurse practitioner and/or exercise physiologist) will be present and available throughout and emergency treatment will be available if it becomes necessary. Testing clearance will be required before enrollment into trial. Exercise Training (ET): There are no significant risks to the subjects in the proposed ET methods. The risks to individuals participating in this portion of the study are no greater than the risks when providing conventional physical therapy services to an individual after stroke. The same precautions and safety guidelines

will be taken that are used in Exercise Centers such as the UAB Center for Exercise Medicine to patient care.

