Clinical Testing: The functional assessments used in the proposed study are routine, clinical assessments of gait and stroke impairments used in stroke outpatient and therapy clinics. The experimental protocol to be used in this portion of the proposal involves minimal risk and is considered standard clinical practice.

MRI Neuroimaging: The MRI scanner contains a very strong magnet. Therefore, participants may not be able to have the MRI if they have certain types of metal implanted in their body, for example, any pacing device (such as a heart pacer), any metal in their eyes, or certain types of heart valves or brain aneurysm clips. Although there is no indication that MRI is unsafe during pregnancy, if the participant is female, she will be asked to take a urine pregnancy test to verify that she is not pregnant. There is not much room inside the MRI scanner. The participant may be uncomfortable if they do not like to be in close spaces ("claustrophobia"). If the participant becomes uncomfortable at any time, they can request that the scan be stopped. All participants will pass an MRI screen to decrease risk of adverse events.

b. Estimate the frequency, severity, and reversibility of each risk listed. Possible physical risks would be serious and possibly not reversible, but are highly unlikely and rare. There is also a possibility of experiencing a localized twitching sensation due to magnetic field changes during rTMS and imaging; this is expected, should not be painful, and is reversible after exiting the magnetic environment. The ET program and the clinical testing should not present a risk for the patient but could result in muscle soreness and/or joint stiffness, but these symptoms should not persist more than a few days. There is a minimal risk for muscle strains during the testing and training.

Assessments/Questionnaires: Risk is minor and readily reversible.

c. Is this a therapeutic study or intervention?

Yes No

If Yes, complete i.-iii.

i. Describe the standard of care in the setting where the research will be conducted: these patients would typically be followed in the Headache or Stroke clinic and be given pharmacologic options to treat their headaches/post-stroke pain.

ii. Describe any other alternative treatments or interventions: continued standard of care treatments with pharmacologic approaches.

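### Inclusion criterion 4 can be met on cycling alone, yet every exercise session prescribes treadmill walking with no cycle-only option, and falling is listed as a risk of the exercise test but not of training

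*Combined protocol and SAP*

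**What the plan says.** **Entry.** Inclusion criterion 4 in section 3.d reads "Ability to walk or tolerate recumbent cycle ergometry for 10 mins", without assistance. Either activity is enough. The disability limit in exclusion criterion 2 is "Pre-stroke modified Rankin >2", so it concerns function before the stroke. Section 2 (Background) says that patients with walking difficulty can still exercise because the stationary cycle lets them reach the target dose.

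**Intervention.** Section 4.a (Exercise sessions) gives one standardized prescription for all participants: "Each session includes a combination of treadmill (TM) walking and stationary cycle ergometry (CE"), with interval and steady-state work. For intolerance or undue fatigue the workload may be reduced, for example by 10%, and the reduction is recorded. A change of machine is not mentioned.

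**Risks.** For the one-off test, section 6.a says "The risks of the exercise tolerance tests are minimal but could include fainting, falling, irregular heartbeat", among other events. For training it says "There are no significant risks to the subjects in the proposed ET methods" and then states that the risk does not exceed that of conventional physical therapy after stroke. Section 6.b adds "The ET program and the clinical testing should not present a risk for the patient", apart from soreness, stiffness and a small risk of muscle strain. A note in section 6.a says "Risks included here should be included in the consent form or information sheet, as applicable".

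**The concern.** Two parts of the plan do not fit together. Eligibility and background allow for people who cannot walk unassisted and rely on the cycle. The session prescription then includes treadmill walking for everyone. A coordinator who follows section 4.a to the letter would put a person admitted on cycling alone onto a treadmill.

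The risk section does not reflect this. It treats falling as a foreseeable harm of a single supervised test but not of repeated sessions that include treadmill walking.

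What is at stake is participant safety and a complete list of risks. There is also a smaller point of interpretation. The hypothesis in section 1.a includes the safety of pairing rTMS with exercise, so a fall in training would count in the safety results. Reading such an event is easier if the machine used in each session is on record.

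**Working it through.** The plan gives no figure on this point and no arithmetic applies. The check is to set the sections side by side.

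1. **Can someone enter without being able to walk unassisted?** On criterion 4 alone, yes, because the two activities are joined by *or*. Exclusion criterion 2 does not prevent it, since it looks only at function before the stroke. Table 1 collects the modified Rankin score at baseline, but no eligibility criterion uses that value.

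2. **Do the other entry requirements show treadmill ability?** Inclusion criterion 7 requires a maximal graded exercise test and clearance. Exclusion criterion 11 removes anyone who fails exercise screening. Section 3.j refers to established clearance criteria, and section 6.a requires clearance before enrollment. The described content of the test is ECG and indirect calorimetry. Whether it is done on a treadmill or a cycle is not stated, and the clearance criteria are not reproduced. These requirements may screen out unsafe walkers, but the documents do not show that they do.

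3. **Is gait assessed elsewhere?** Section 6.a (Clinical Testing) says "The functional assessments used in the proposed study are routine, clinical assessments of gait and stroke impairments". Table 1 lists a physical examination, the modified Rankin score and a stroke scale, but names no gait or balance test. No such finding is tied to treadmill use.

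4. **Does the session allow the cycle alone?** Section 2 suggests that this is the intention. Section 4.a does not say so, and its one stated adjustment is to workload.

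5. **Is falling listed for training?** No. It is named for the test in section 6.a. For training, sections 6.a and 6.b name soreness, stiffness and strain. Section 6.b opens with a general remark about rare but serious physical risks, without naming falls.

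6. **Could there be a reason for the difference?** Supervision is not one, because professional staff also attend the test and falling is still listed there. The instruction in section 6.a to omit risks of standard-of-care procedures is not one either. Section 6.c describes standard care here as clinic follow-up with drug treatment, so training is a research procedure.

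7. **Do the stopping rules cover it?** Sections 4.a and 7.b name heart rate, blood pressure, angina, light-headedness, confusion, dyspnea and the participant's wish. Loss of balance is not named, although the list in section 7.b is not presented as exhaustive.

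**The case against.** The strongest reply is that the plan already has several layers of protection. Every participant must pass a maximal exercise test and be cleared. Sessions are fully supervised. Section 6.a promises the precautions used in exercise centers. Section 7.b adopts recognized termination criteria by reference and ends a session if an unforeseen hazard arises. The comparison with conventional physical therapy can be read as covering falls implicitly, and section 2 shows that the cycle is there for people who walk poorly. All of this stands as mitigation, and it makes a literal and unsafe use of section 4.a less likely. It does not supply the missing permission to use the cycle alone, and a comparison of risk does not tell anyone what the risk is.

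A reader might infer more than the documents support:

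- *That participants are not told about falls.* The consent pages are not available. The note in section 6.a says that listed risks should go into the consent form; it does not limit the form to them.
- *That falls would go unrecorded.* Table 1 schedules adverse events weekly and at one month, and section 7.b records any adverse event, so a fall would be captured whether or not it was listed in advance.
- *That the comparison of arms is biased.* Both arms receive the same exercise.
- *That the total of planned sessions measures the problem.* That total counts everyone randomized. The people at issue are those admitted on cycling alone, and after clearance there may be none.

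**Conclusion.** The point holds as a mismatch between the eligibility rule and the session prescription, together with an incomplete list of training risks. It deserves correction because a stated rule, followed exactly, gives a worse safety result than the plan's own rationale intends. It is more than a missing detail, but it is modest in weight.

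Its size cannot be put in numbers. The documents give neither the number of participants unable to walk unassisted nor a fall rate, and no estimate is offered for either. The conclusion assumes that section 4.a means what it says for all participants, and that the unseen clearance criteria do not already require treadmill ability. If they do, the session wording becomes a matter of clarity, but the omission of falls from the training risks remains.

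Sample size, endpoints and analysis are not affected.

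**What to change.** 1. **Section 4.a, Exercise sessions.** Add: *Participants who, in the judgment of the supervising clinician, cannot safely walk on a treadmill complete the session on the cycle at the same heart-rate target. The mode used is recorded at each session.* This agrees with section 2, which defines dose by the physiologic target reached more than by time or repetitions.

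2. **Sections 6.a and 6.b.** Replace the statements that training carries no significant risk with: *Training can cause falls, including on the treadmill, as well as muscle soreness, joint stiffness and muscle strain.* Carry this to the consent form if it is not already there.

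3. **Optional stopping criterion.** If one is added, limit it to *new or worsening unsteadiness during treadmill walking*, with a switch to the cycle. A general rule on unsteady gait would be a mistake: some participants could meet it on arrival, and it would stop exercise for the very people whom the first change moves to the cycle.

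The cost is a few sentences and one extra field on the session record. The downside is a slightly less uniform exercise mode across participants. Sample size, visits and analysis stay as they are.
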